2.1 Study endpoints**Primary endpoints:**

- Asymptomatic GAS throat and skin carriage and clinical GAS infection prevalence at each monthly visit
- Asymptomatic GAS throat and skin carriage and clinical GAS infection incidence per person year
- Duration of asymptomatic GAS throat and skin carriage to the nearest week
- Phylogenetic relatedness of GAS isolates by whole genome sequencing
- Clinical examination findings and features of clinical GAS infection

Secondary endpoints:

- Presence of risk factors for GAS carriage or disease at individual and household levels
- Seasonal variation in GAS carriage and infection prevalence
- GAS *emm* type
- Groups C and G streptococcal prevalence and incidence
- Quantification of bacterial presence by qPCR
- GAS serological responses (including seroprevalence and fold-change in antibody titres in response to asymptomatic carriage and clinical infection).
- GAS presence on household swabbing and settle plates
- GAS antimicrobial sensitivity

3 Study design

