7.2 Study discontinuation

In the event that the study can no longer continue safely due to any reason, such as MRCG limiting research activities or The Gambia Government introducing new public health restrictions which make the study unable to continue, the study will be discontinued following a decision by the PI, study team and co-investigators.

8 Statistical considerations

The primary outcome measures used to determine sample size were:

1. GAS carriage prevalence, and
2. GAS carriage incidence over 12 months.

In HIC, GAS pharyngeal carriage prevalence in children is 2-17%(12, 13), and in Uganda is 15.9% (29). Our study also includes adults, in whom carriage is lower, but will use pooled skin and pharyngeal carriage as our outcome measure, which will likely increase prevalence in turn. **We therefore estimate a pooled prevalence of 15%.**

GAS pharyngeal carriage yearly incidence in children in the US was shown to be 27-32% (12). We found a skin infection incidence of 592/1000 child years in The Gambia during an influenza vaccine study follow-up (unpublished data) and of which ~50% are likely due to GAS (30). As we are including adults with a likely lower incidence, **we estimate a yearly incidence of 20%.**

The sample size was calculated for the primary objective, GAS carriage prevalence, using the formula below to measure the estimated prevalence of 15% with a precision of $\pm 5\%$.

[figure not shown]
$$n = \frac{Z_{\alpha/2}^2 \times p \times (1 - p)}{e^2}$$

Where p is predicted proportion and e is desired precision.

Using $Z=1.96$ for $\alpha=0.05$, $p=0.15$ and $e=0.05$ we require a sample of 196. Intracluster correlation is unknown, **therefore we used a conservative design effect of 2**, which allowing for 10% drop-out rate gives a required sample size of 431.

We therefore propose to recruit 45 households, which with an average household size of 10, will equal approximately 450 individuals for the main cohort.

This sample size would provide adequate power for precise estimates of prevalence and incidence of GAS carriage and to detect risk factors for GAS carriage (Figures E-G).

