Sample size simulations. E: Assuming a design effect of 2, the selected sample size of n=444 would have precision of between ± 4 and $\pm 5\%$ to detect a GAS carriage prevalence of 15%. F: The selected sample size of n=444 would have $>80\%$ power to detect risk factors associated GAS carriage with prevalence or risk ratios of 2, 2.5 and 3. G: The sample size would have a precision of between ± 4 and $\pm 5\%$ to detect a GAS carriage incidence of 20% per person year.

9 Data handling and record keeping

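### Section 8, caption G: the stated incidence precision of ±4 to ±5% does not hold at the protocol's only design effect, 2 (about ±5.9 points as a rate, ±5.3 as a 12-month risk)

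*Protocol*

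**What the plan says.** Section 8 names two outcomes used to set the sample size: carriage prevalence and "GAS carriage incidence over 12 months". The derivation itself is for the first: "The sample size was calculated for the primary objective, GAS carriage prevalence". Because the intracluster correlation is not known, "therefore we used a conservative design effect of 2", and with 10% drop-out the requirement comes to 431. For the second outcome the text says "we estimate a yearly incidence of 20" per cent and gives no separate allowance for clustering.

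The text then concludes: "This sample size would provide adequate power for precise estimates of prevalence and incidence of GAS carriage", citing Figures E to G. Caption E begins "Assuming a design effect of 2, the selected sample size of n=444 would have precision of between" and gives ±4 to ±5% for a prevalence of 15%. Caption G gives the same ±4 to ±5% "to detect a GAS carriage incidence of 20% per person year", with no design effect in its wording.

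Section 2.1 lists as a primary endpoint "Asymptomatic GAS throat and skin carriage and clinical GAS infection incidence per person year".

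**The concern.** Captions E and G print an identical precision for two different quantities, 15% prevalence and 20% incidence, measured in the same people in the same households of about 10. Caption E states its clustering allowance; caption G does not. At the same sample size and design effect, the interval around 20% must be wider than the interval around 15%, and wider still if the 20% is a rate per person-year. So either caption G uses a smaller design effect than caption E, or its range is too narrow.

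Incidence per person-year is a primary endpoint, and section 8 relies on both captions for its statement on precision. A reader will take prevalence and incidence to be equally well estimated under the same household-clustering allowance. At a design effect of 2 they are not.

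**Working it through.** **Inputs (protocol, section 8 unless stated)**

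- Z = 1.96
- n = 444 (caption E; caption G refers to the same sample size)
- Incidence 0.20 per person-year (caption G), or 20% yearly (text)
- Prevalence 15%
- Design effect (DE) 2, the only value given
- Average household size 10
- Follow-up 12 months (section 3.1), so about 444 person-years (PY) if everyone contributes a full year at risk

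**Formulas for the 95% half-width**

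- Rate: 1.96 × √(DE × 0.20 / PY)
- Risk or prevalence: 1.96 × √(DE × p(1 − p) / n)

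**Step 1: the protocol's other figures reproduce.** 1.96² × 0.15 × 0.85 / 0.05² = 195.9, so 196; 196 × 2 × 1.1 = 431.2, so 431. Caption E: 1.96 × √(2 × 0.15 × 0.85 / 444) = ±4.70 points, inside ±4 to ±5. Without the design effect it is ±3.32, outside. Caption E therefore depends on the design effect of 2.

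**Step 2: caption G.**

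| Reading of 20% | DE = 1 | DE = 2 |
|---|---|---|
| Rate, 0.20 per person-year | ±4.16 | ±5.88 |
| 12-month risk, p = 0.20 | ±3.72 | ±5.26 |
| Rate converted to risk, p = 1 − e^(−0.20) = 0.181 | ±3.58 | ±5.07 |

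The rate with no clustering allowance falls inside the stated range. Nothing in the DE = 2 column does. For the rate at DE = 2 the interval is 20 ± 5.88, or 14.1 to 25.9 per 100 person-years. Other interval methods at DE = 2 (effective n = 222) do not change this: exact Poisson has a half-width of about ±6.13 for the rate, and for the 20% risk Wilson gives ±5.24 and Clopper-Pearson ±5.46.

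**Step 3: which design effects fit caption G?** Setting the half-width to 0.05 and solving:

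- Rate: 0.05² × 444 / (1.96² × 0.20) = 1.44
- Risk of 20%: 0.05² × 444 / (1.96² × 0.16) = 1.81

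Setting it to 0.04 gives 0.92 for the rate, so DE = 1 is already inside the range, and 1.16 for the risk. Caption G therefore holds for a design effect up to about 1.44 (rate) or between about 1.16 and 1.81 (risk of 20%). For the converted risk the upper limit is 1.95.

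**Step 4: person-time.** A full year at risk for everyone is favourable to the plan. As an illustration only, removing the 15% expected to carry at baseline leaves 444 × 0.85 = 377, which at DE = 2 gives ±6.38 (rate) or ±5.71 (risk). With no clustering allowance the rate stays inside caption G's range even with less person-time: ±4.38 at 400 person-years, ±4.51 at 377, and ±4.76 at 340 (444 × 0.85 × 0.9). The mismatch thus comes from the clustering allowance and not from the person-time assumed.

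**The case against.** The strongest reply is that caption G reproduces on its own terms. It names a rate, a sample size and no design effect, and those inputs give ±4.16. The design effect of 2 is introduced in a calculation for prevalence, is described as conservative, and is nowhere said to apply to incidence. Using design effect = 1 + (10 − 1) × ICC, the limits of 1.44 and 1.81 correspond to intracluster correlations of 0.44/9 = 0.05 and 0.81/9 = 0.09, and the text excludes neither. The graph is not shown and may carry its own label. On a risk reading, ±5.26 and ±5.07 both round to ±5. Finally, no decision turns on the figure, because section 8 sets no numerical precision target for incidence.

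Much of this stands as a limit on the point. Carrying 2 over to incidence is an assumption, the missing graph could show a smaller value, and the excess is modest. The illustration with 377 people at risk is not a bound either: section 3.2.2 counts someone as newly positive after a negative result at the previous visit, so a baseline carrier who clears can become at risk again.

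It does not remove the point. The same households supply both outcomes, 2 was chosen because the correlation is unknown, and section 8 uses Figures E to G jointly to support precision for both outcomes. If caption G was drawn with 2, its range is wrong. If it was drawn with less, the text neither gives nor defends the value. Rounding helps only the risk readings; caption G and the primary endpoint both name a rate per person-year, for which the figure is ±5.9.

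**Conclusion.** The concern holds. At the protocol's only stated design effect, the incidence precision at n = 444 is about ±5.9 points as a rate or ±5.3 points as a 12-month risk of 20%, not ±4 to ±5. The excess over ±5 runs from 0.07 points (rate converted to an 18.1% risk) to 0.9 points (rate). The printed range needs a design effect no larger than about 1.44 for the rate or 1.81 for a 20% risk, and the text supports neither.

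This rests on two assumptions: that the design effect of 2 carries over to incidence, because the text offers no other, and that each of the 444 contributes a full year at risk. The second favours the plan. Confidence is moderate because the graph cannot be seen. The point concerns the stated figure and not the adequacy of the sample: the required 431, the planned 45 households and caption E are unaffected. It should be corrected, since it misdescribes the precision of a primary endpoint.

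**What to change.** Restate caption G at design effect 2 as about ±5.9 points for a rate of 0.20 per person-year, or ±5.3 points if a 12-month risk of 20% is meant. Alternatively, keep the present range, state the smaller design effect used for incidence and justify it. In either case:

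- say whether the quantity is a rate or a 12-month risk;
- note, without a numerical maximum, that drop-out, late enrolment and exclusion of baseline carriers from the time at risk would widen the interval further;
- make the sentence in section 8 that cites Figures E to G refer to the restated incidence precision.

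The cost is one caption and one sentence. Enrolment, the 431 and the prevalence precision do not change. The only downside is a slightly less favourable stated precision for incidence.

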9.1 Unique study ID numbers

Each household on the GPS location list will be given a household ID number (HID) which will be three digits long (e.g. 001, 002). This number will not change regardless of whether the household provides consent and is enrolled or not. The HID will be recorded on the sensitization form and sensitization log book when the household undergoes sensitization. If a household reaches the stage of informed consent, each ICD will be documented with the HID number at the top. Each household member who then consents will be given, at that point, a two digit individual study number (e.g. 01, 02, 03), according to the number of household members and the order in which they are consented. The two digit individual study number will be recorded on that individual's ICD, in addition to the HID.

All consented individuals will then have a unique participant ID number (PID) consisting of the three HID digits (e.g. 004), followed by their two digit individual study number (e.g. 02), and then a check digit calculated by the Damm algorithm (e.g. F). Their PID number will therefore consist of 5 numbers and one letter (e.g. 00402F). This number is unique to each participant in the study, and will be

recorded on every CRF and other study document completed by the study team. After sensitization and consent, no participant identifiable data will be recorded, and participants will only be identified by their PID.

9.2 Data management and processing

Field data will be collected on electronic case report forms (eCRF) inputted on tablet computers by the field team. The questionnaires will be designed using REDCap™ electronic data capture software hosted at MRCG. Data will be collected offline and synced with the secure database at the end of each day. Data generated in the laboratory will be inputted onto the same database. Written informed consent will be sought from all participants prior to any study activities and before any data is collected.

Questionnaires will be designed with up-front data quality checks including reference ranges and dropdown menus to minimise incorrect data entry. Additionally, after completion of the study, a data checking process will be performed running queries to check for incomplete or nonsense data.

All data will be kept confidentially, and electronic data encrypted. Each participant will be assigned a unique study ID, so that no person identifiable data will be kept on the database. Any person identifiable data will be held securely and will not be available to anyone other than those in the investigator team.

9.3 Data sharing and access

Data will be handled in accordance with the data management SOPs of MRCG which is fully compliant with GDPR regulations. All documents used will be version controlled and dated. Anonymised data will be held in the study database for a minimum of 10 years following project completion, in compliance with LSHTM's Records Retention and Disposal Schedule. Anonymised raw study data and analysis code will be deposited in the LSHTM Data Compass repository on publication of study outputs, and will be available upon request for scientific purposes.

Whole genome sequencing data will be generated using the illumina Miseq platform at MRCG. Raw sequence data will be in the form of fastq files and initially stored on the high performance cluster (HPC) at MRCG. Data management and analysis will be performed on pipelines established on both the MRCG HPC, as well as cloud-based servers such as the MRC CLIMB platform (used currently by [name]'s group and others at MRCG). Raw sequence data will be archived at MRCG according to their data archiving procedures. Certain processed data fields from genomic analysis (e.g. emm type) will be included as variables in the study REDCap™ database. Sequence data along with links to relevant metadata will be submitted to a public sequence repository (e.g. genbank) as is standard practice, on publication of study outputs. Analysis pipeline and code will be made openly available via GitHub on publication of the study.

9.4 Source documents and access to source data

The Principal Investigator will maintain appropriate medical and research records for this study in compliance with the principles of good clinical practice and regulatory and institutional requirements for the protection of confidentiality of participants. The study team members will have access to records.

The authorised representatives of the sponsor, the ethics committee(s) or regulatory bodies may inspect all documents and records required to be maintained by the investigator, including but not limited to, medical records (office, clinic, or hospital) for the participants in this study. The clinical study site will permit access to such records.

10 Ethical considerations

This study is conducted in accordance with the principles set forth in the ICH Harmonised Tripartite Guideline for Good Clinical Practice and the Declaration of Helsinki in its current version (see appendix), whichever affords the greater protection to the participants.

Ethical approval for the study will be sought from the MRC Scientific Coordinating Committee and the joint MRC/Gambia Government Research Ethics Committee. As described above, RHD carries a significant economic and health burden in The Gambia, as do superficial GAS infections. The results of the study will contribute valuable information to the global scientific community, as well as to policy makers in The Gambia. By raising awareness of the burden of these common infections and the importance of reducing GAS carriage and transmission, the study aims to provide a basis for future work which will focus on reduction strategies.

10.1 General considerations on human subject protection

10.1.1 Rationale for participant selection

Since GAS carriage and infection can be present in anyone, regardless of age or sex, we chose not to exclude anyone on these bases. Sukuta is the site of recruitment as this builds on our previous data from this area. Selection of households for participation will be done by random geographical selection. A set of random GPS coordinates within Sukuta will be generated, and the study team will approach the nearest household to that location for participation. For the purposes of enrolment in the study, a household will be defined according to The Gambia Demographic and Health Survey 2013 definition: “a household [is] defined as a person or a group of related or unrelated persons who live together in the same dwelling unit(s) or in connected premises, who acknowledge one adult member as the head of the household, and who have common arrangements for cooking and eating.”

We made the decision to exclude households with fewer than 3 members and those without any children, as smaller households would make household transmission analysis less relevant and may not provide information about within household transmission that we require.

10.1.2 Evaluation of risks and benefits

Risks:

There is a small risk of discomfort to individuals during the sampling procedures. Taking of oropharyngeal and pyoderma wounds swabs may be slightly uncomfortable, but is safe and brief. Salivary samples are collected using foam oracle swabs which do not hurt at all. Dried blood spot collection may be uncomfortable due to a pinprick with a lancet, and blood serum collection may cause mild discomfort and a slight bruise.

Apart from sampling discomfort, some of the questions asked may feel slightly intrusive to the participants, including asking about social mixing behaviour, however it will always be made clear to participants that they can choose not to answer any question.

Benefits:

The benefit to the participants and their household is that they will have regular visits from nurses examining them for evidence of GAS infections and other medical problems. Any GAS infections and some other common medical problems will be provided with treatment at the household visits. They will therefore receive regular medical check-ups over the course of enrolment in the study, likely resulting in prompt diagnosis of any medical problems.

Furthermore, participants will have access to the doctors and nurses of the study on-call team in case of any medical problem that may arise, who can advise them what to do, provide prescriptions or referrals as appropriate to ensure that participants receive the best level of local care available.

The community and country additionally stand to benefit from the findings of the study in that they will inform future GAS control strategies in countries such as The Gambia, and the study will place the community in an ideal position to be considered as a site for potential future GAS vaccine trials.

10.2 Informed consent

Written informed consent will be obtained before any study activities are undertaken. The informed consent document (ICD) will be read line-by-line to the participant or participant's parent/guardian in the language of their choice. If they agree to participate, they will be asked to sign (or thumbprint) the consent form. If the parent has more than one eligible child, they will be asked to sign a consent form for each child. The option to consent for the future use of samples on study completion will also be given on the same page but the provision of such additional consent is not required for participation in the main trial. The ICD will make clear the purpose of the study, include information about the use of the samples, and describe the extent of the examination required. Participants will be free to withdraw from the study at any time without giving a reason

10.3 Participant confidentiality

Participants' identifiable data such as names, and telephone numbers will be kept in separate log books and utility databases separate from the overall study database. Access to these logs and databases will be controlled, ensuring that only the necessary persons have access to participants personal details. All study data collected will be anonymised and linked to the individual's unique PID number (see section 9.1).

10.4 Future use of stored specimen

The informed consent documents will contain an option for participants to consent for the future use of samples collected in the study for additional research, and it will be made clear to participants during their informed consent process that their choice in this matter does not affect their involvement in any other way.

11 Financing and insurance

The study will be funded by the PI's clinical PhD fellowship award through the Wellcome Trust via LSHTM. Additional funding will be sought for additional analyses of samples, and other study activities which may be possible following submission of protocol amendments, where possible from other funding sources.

12 Publication policy

During the study design and protocol preparation we will maintain contact with a number of collaborators in the GAS field around the world, and at MRCG. This will allow us to refine the research design and endpoints according to advice and new evidence that might emerge before the start of the study.

The study results will be published promptly in peer-reviewed journals and promoted through the MRC communications department and strategy and through social media where appropriate. Data will be submitted as abstracts to be presented at international conferences such as the European Congress of Clinical Microbiology and Infectious Diseases and the Lancefield International Meeting on Streptococci and Streptococcal Disease.

The PI I will be the corresponding author on all published articles and will be available to discuss the results and data.

13 References

Appendix: Revised Jones Criteria (from CDC)

[figure not shown]
Table: Revised Jones Criteria for diagnosing acute rheumatic fever

Part A. For all patient populations with evidence of preceding group A strep infection		
Diagnosis: Initial ARF	2 major manifestations or 1 major plus 2 minor manifestations	
Diagnosis: Recurrent ARF	2 major manifestations or 1 major plus 2 minor manifestations or 3 minor manifestations	
	Low-risk populations*	Moderate- and high-risk populations*
Part B. Major manifestations	Carditis 
 • Clinical and/or subclinical Arthritis 
 • Polyarthritis only Chorea Erythema marginatum Subcutaneous nodules	Carditis 
 • Clinical and/or subclinical Arthritis 
 • Monoarthritis or polyarthritis • Polyarthralgia (if other causes have been excluded) Chorea Erythema marginatum Subcutaneous nodules
Part C. Minor manifestations	Polyarthralgia Fever ($\geq 38.5^{\circ}\text{C}$) Elevated acute phase reactants (ESR ≥ 60 mm in the first hour and/or CRP ≥ 3.0 mg/dl) Prolonged PR interval on electrocardiography, after accounting for age variability (unless carditis is a major criterion)	Monoarthralgia Fever ($\geq 38^{\circ}\text{C}$) Elevated acute phase reactants (ESR ≥ 30 mm/hr and/or CRP > 3.0 mg/dl) Prolonged PR interval on electrocardiography, after accounting for age variability (unless carditis is a major criterion)

ARF = acute rheumatic fever; ESR = erythrocyte sedimentation rate; CRP = C-reactive protein; mm = millimetres; mg/dl = milligrams per decilitre

*Low-risk population is defined as an acute rheumatic fever incidence of ≤ 2 per 100,000 school-aged children or all age rheumatic heart disease prevalence of ≤ 1 per 1000 population per year. Those not included in the low-risk population are defined as moderate or high risk depending upon their reference population.

Schematic of Study Design:

